## Summary of Changes to the Protocol

The previous version of this protocol (Version 2.0, 12 July 2021) was amended to create the current version (Version 3.0, 19 August 2021). The protocol history is provided below.

Protocol History	
Version and Date of Protocol	Comments
Version 1.0, 27 April 2021	Original version
Version 2.0, 12 July 2021	Added exclusion criteria that subjects cannot participate in an interventional study of a non-investigational treatment from screening through end of study participation; Updated acceptable methods of contraception based on supporting nonclinical data
Version 3.0, 19 August 2021	Current version

Key changes in the current version of the protocol are summarized below.

Change and Rationale	Affected Sections
Expanded study population to include subjects who have at least 1 CFTR mutation identified as responsive to ELX/TEZ/IVA based on in vitro data and no F508del mutation (TCR/non-F) (in addition to subjects homozygous for F508del or heterozygous for F508del and either a gating or residual function mutation).	Global
Increased planned sample size and Treatment Period duration	Global
Study endpoints were updated to reflect the change in Treatment Period duration	Sections 2, 7, and 12.3.3
Liver function test elevations, creatine kinase elevations, rash, cataracts, hypoglycemia, and neuropsychiatric events were designated as adverse events of special interest	Section 12.3.4
Hemoglobin A1c was added to the hematology panel to assess pancreatic endocrine function	Section 9.3.4, Table 3-1, Table 3-2, and Table 11-2
Analysis of primary and key secondary endpoints through Week 24 will be estimated by averaging Weeks 16 and 24	Sections 2 and 12.3.3.1
Stratification by genotype group was updated to be based on F/F, F/G, F/RF, and TCR/non-F genotypes	Sections 2, 9.2, and 12.3.3
Rationale for the non-inferiority margin for primary analysis of the primary endpoint was provided	Section 12.1
Clarified that it is the responsibility of the investigator to report unexpected serious adverse drug reactions to the local IRB/IEC if allowed by local regulations	Section 13.1.2.3

Typographical and administrative changes were also made to improve the clarity of the document.

## 2 PROTOCOL SYNOPSIS

**Title** A Phase 3, Randomized, Double-blind, Controlled Study Evaluating the Efficacy and Safety of VX-121 Combination Therapy in Subjects With Cystic Fibrosis Who Are Homozygous for *F508del*, Heterozygous for *F508del* and a Gating (F/G) or Residual Function (F/RF) Mutation, or Have At Least 1 Other Triple Combination Responsive *CFTR* Mutation and No *F508del* Mutation

**Brief Title** A Phase 3 Study of VX-121 Combination Therapy in Subjects With Cystic Fibrosis Who Are Homozygous for *F508del*, Heterozygous for *F508del* and a Gating (F/G) or Residual Function (F/RF) Mutation, or Have At Least 1 Other Triple Combination Responsive *CFTR* Mutation and No *F508del* Mutation

**Clinical Phase and Clinical Study Type** Phase 3, efficacy and safety

**Objectives Primary Objective**

To evaluate the efficacy of VX-121/tezacaftor/deutivacaftor (VX-121/TEZ/D-IVA) in cystic fibrosis (CF) subjects who are homozygous for *F508del*, heterozygous for *F508del* and a gating (F/G) or residual function (F/RF) mutation, or have at least 1 other triple combination responsive (TCR) *CFTR* mutation and no *F508del* mutation

**Secondary Objectives**

- To evaluate the safety of VX-121/TEZ/D-IVA
- To evaluate the pharmacokinetics (PK) of VX-121/TEZ/D-IVA

**Endpoints Primary Endpoint**

Absolute change from baseline in percent predicted forced expiratory volume in 1 second (ppFEV1) through Week 24

**Key Secondary Endpoints**

- Absolute change from baseline in sweat chloride (SwCl) through Week 24
- Proportion of subjects with SwCl <60 mmol/L through Week 24 (pooled with data from Study VX20-121-102)
- Proportion of subjects with SwCl <30 mmol/L through Week 24 (pooled with data from Study VX20-121-102)

**Other Secondary Endpoints**

- Number of pulmonary exacerbations (PEX) through Week 52
- Absolute change from baseline in Cystic Fibrosis Questionnaire – Revised (CFQ-R) Respiratory Domain (RD) score through Week 24
- Absolute change from baseline in ppFEV1 through Week 52
- Absolute change from baseline in SwCl through Week 52
- Proportion of subjects with SwCl <60 mmol/L through Week 24
- Proportion of subjects with SwCl <30 mmol/L through Week 24
- Safety and tolerability assessments based on adverse events (AEs), clinical laboratory values, ECGs, vital signs, and pulse oximetry

[figure not shown]
**Other Endpoints**

- Proportion of subjects with SwCl <60 mmol/L through Week 52
- Proportion of subjects with SwCl <30 mmol/L through Week 52
- Absolute change from baseline in body mass index (BMI) at Week 52
- Absolute change from baseline in BMI z-score at Week 52
- Absolute change from baseline in weight at Week 52
- Absolute change from baseline in CFQ-R RD score through Week 52
- PK parameters of VX-121, TEZ, and D-IVA

Number of Subjects	Approximately 550 subjects will be randomized (1:1) to the VX-121/TEZ/D-IVA group or the elxacaftor (ELX)/TEZ/ivacaftor (IVA) group.
Study Population	Male and female subjects with CF who are 12 years of age or older with the following genotypes: homozygous for F508del ; heterozygous for F508del and either a gating (F/G) or residual function (F/RF) mutation; or at least 1 TCR mutation identified as responsive to ELX/TEZ/IVA and no F508del mutation (TCR/non-F).
Investigational Drug	
Study drug refers to VX-121/TEZ/D-IVA, ELX/TEZ/IVA, IVA, and their matching placebos.
 
Active study drugs will be orally administered as either 2 fixed-dose combination (FDC) film-coated VX-121/TEZ/D-IVA tablets in the morning, or as 2 FDC film-coated ELX/TEZ/IVA tablets in the morning and as 1 film-coated IVA tablet in the evening.
 
Active substance: VX-121, TEZ (VX-661), and D-IVA (VX-561)
 
Activity: CFTR corrector, CFTR corrector, and CFTR potentiator (increased Cl secretion)
 
Strength and route of administration: 10 mg VX-121/50 mg TEZ/125 mg D-IVA; oral administration
 
Active substance: ELX (VX-445), TEZ (VX-661), and IVA (VX-770)
 
Activity: CFTR corrector, CFTR corrector, and CFTR potentiator (increased Cl secretion)
 
Strength and route of administration: 100 mg ELX/50 mg TEZ/75 mg IVA; oral administration
 
Active substance: IVA (ivacaftor; VX-770)
 
Activity: CFTR potentiator (increased Cl secretion)
 
Strength and route of administration: 150 mg; oral administration

Study Duration	The total study duration is approximately 64 weeks (4 weeks for the Screening Period, 4 weeks for the Run-in Period, 52 weeks for the Treatment Period, and 4 weeks for the Safety Follow-up Period).
Study Design	
This is a Phase 3, randomized, double-blind, ELX/TEZ/IVA-controlled, parallel-group, multicenter study.
 
All subjects entering the Run-in Period will receive ELX 200 mg qd/TEZ 100 mg qd/IVA 150 mg every 12 hours (q12h). Following completion of the Run-in Period, approximately 550 subjects will be randomized (1:1) to the VX-121/TEZ/D-IVA group or ELX/TEZ/IVA

group. The dosages to be evaluated are shown in the table below. Randomization will be stratified by age at the Screening Visit (<18 versus ≥18 years of age), ppFEV1 determined during the Run-in Period (Day -14 clinic assessment; <70 versus ≥70), SwCl determined during the Run-in Period (Day -14 assessment; <30 versus ≥30 mmol/L), prior CFTR modulator use (yes versus no), and genotype group (F/F, F/G, F/RF, and TCR/non-F).

**Figure 2-1 VX20-121-103 Study Design**

D-IVA: deutivacaftor; ELX: elexacaftor; IVA: ivacaftor; N: number of subjects; TEZ: tezacaftor

Note: The figure is not drawn to scale.

**Treatment Groups and Dosages**

Treatment Group	VX-121	ELX	TEZ	D-IVA	IVA
VX-121/TEZ/D-IVA	20 mg qd	0 mg	100 mg qd	250 mg qd	0 mg
ELX/TEZ/IVA	0 mg	200 mg qd	100 mg qd	0 mg	150 mg q12h

D-IVA: deutivacaftor; ELX: elexacaftor; IVA: ivacaftor; q12h: every 12 hours; qd: once daily; TEZ: tezacaftor

- Assessments**
  - Efficacy:** Spirometry, SwCl, CFQ-R, documentation of events related to health outcomes (e.g., PEx), height, and weight
  - Safety:** AEs, clinical laboratory assessments, ECGs, vital signs, pulse oximetry, physical examinations, and ophthalmologic examinations (for subjects <18 years of age on the date of informed consent)
  - PK:** VX-121, TEZ, D-IVA, ELX, IVA, and relevant metabolite plasma concentrations
  - Exploratory:** Treatment Satisfaction Questionnaire for Medication (TSQM), Cystic Fibrosis Impact Questionnaire (CF-IQ), DNA sample (optional), inflammatory mediators, blood biomarker sample, RNA sample (optional), and sputum samples

**Statistical Analyses** The primary efficacy endpoint is the absolute change from baseline in ppFEV1 through Week 24 (estimated by averaging Weeks 16 and 24). The primary null hypothesis to be tested is that the mean absolute change from baseline in ppFEV1 through Week 24 for VX-121/TEZ/D-IVA is inferior by >3 percentage points compared to ELX/TEZ/IVA. The null hypothesis will be tested at a 1-sided significance level of 0.025.

Assuming a within-group SD of 8 and 10% drop-out rate at Week 24 and a treatment difference of 0 between VX-121/TEZ/D-IVA and ELX/TEZ/IVA, a sample size of 275 subjects in each group for a total of 550 subjects will have more than 95% power to test the primary hypothesis for the primary endpoint, based on a 1-sided, 2-sample *t*-test at a significance level of 0.025.

The primary analysis of the primary endpoint will be conducted with clinic spirometry data only and will be performed using a mixed-effects model for repeated measures (MMRM) with absolute change from baseline in ppFEV1 at Day 15, Week 4, Week 8, Week 16, and Week 24 as the dependent variable. The model will include treatment group, visit, and treatment-by-visit interaction as fixed effects, with continuous baseline ppFEV1, continuous baseline SwCl, age at screening (<18 versus ≥18 years of age), and genotype group (F/F, F/G, F/RF, and TCR/non-F) as covariates. An unstructured covariance structure will be used to model the within-subject errors.

The primary result obtained from the model will be the estimated treatment difference through Week 24. The primary null hypothesis will be rejected and non-inferiority demonstrated if the lower bound of the 95% CI is ≥-3.0.

**DMC Reviews** A data monitoring committee (DMC) will conduct safety reviews of study data as outlined in the DMC Charter.

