##### **12.3.3.1 Analysis of Primary Endpoint**

The primary efficacy endpoint is the absolute change from baseline in ppFEV1 through Week 24 (estimated by averaging Weeks 16 and 24). The primary analysis will be conducted with clinic spirometry data only and will be performed using a mixed-effects model for repeated measures

(MMRM) with absolute change from baseline in ppFEV1 at Day 15, Week 4, Week 8, Week 16, and Week 24 as the dependent variable. The model will include treatment group, visit, and treatment-by-visit interaction as fixed effects, with continuous baseline ppFEV1, continuous baseline SwCl, age at screening (<18 versus ≥18 years of age), and genotype group (F/F, F/G, F/RF, TCR/non-F) as covariates; if there is non-convergence due to small number of subjects in either F/G, F/RF, or TCR/non-F, the genotype group will be considered with two levels: F/F and non-F/F. The model will be estimated using restricted maximum likelihood. Denominator degrees of freedom for the F test for fixed effects will be estimated using the Kenward-Roger approximation. An unstructured covariance structure will be used to model the within-subject errors. If the model estimation does not converge, a compound symmetry covariance structure will be used instead. Conditional on the observed data and covariates, missing data will be assumed to be missing at random; therefore, no imputation of missing data will be performed.

The primary result obtained from the model will be the estimated treatment difference through Week 24. The adjusted mean with a 2-sided 95% CI will be provided. The primary null hypothesis will be rejected and non-inferiority demonstrated if the lower bound of the 95% CI is ≥-3.0. The estimated within group change from baseline and the treatment difference at each post-baseline visit will also be provided, obtained from the model.

The primary null hypothesis of non-inferiority described above will be tested based on the FAS.

If the lower bound of the 95% CI is greater than 0, then superiority for the primary endpoint is demonstrated and the 2-sided *P* value for superiority will be calculated.

Sensitivity analyses for handling missing data will be described in the SAP.

Supportive analyses and subgroup analyses (as appropriate) will also be described in the SAP.

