### 8.3.1.3 Primary Analysis

The primary null hypothesis to be tested is that the mean for the primary efficacy variable for VNZ/TEZ/D-IVA is inferior by >3 percentage points compared to ELX/TEZ/IVA. The primary analysis of the primary estimand will be performed using a mixed-effects model for repeated measures (MMRM) with change from baseline at Day 15, Week 4, Week 8, Week 16, and Week 24 as the dependent variable. The model will include fixed categorical effects for treatment, visit, age at screening (<18 versus ≥18 years of age), genotype group (F/F, F/G, F/RF, TCR/non-F), and treatment-by-visit interaction, with baseline ppFEV1 and baseline SwCl as continuous covariates. The model will be estimated using restricted maximum likelihood. Denominator degrees of freedom for the *F*-test for fixed effects will be estimated using the Kenward-Roger approximation. An unstructured covariance structure will be used to model the within-subject errors. If the model estimation does not converge, genotype group will be considered with two levels (F/F and non-F/F) or removed from the model, and if non-convergence persists, an alternative covariance structure like compound symmetry will be used. Conditional on the observed data and covariates, missing data will be assumed to be missing at random (MAR).

The primary result obtained from the model will be the estimated treatment difference through Week 24 (estimated by averaging Weeks 16 and 24). The adjusted mean with a 2-sided 95% CI and the 1-sided *P* value for non-inferiority will be provided. The primary null hypothesis will be rejected, and non-inferiority demonstrated, if the lower bound of the CI is ≥-3.0.

The primary null hypothesis of non-inferiority described above will be tested based on the FAS.

If non-inferiority for the primary endpoint is demonstrated, and if the lower bound of the same 95% CI is greater than 0, then superiority for the primary endpoint is also demonstrated, and the 2-sided *P* value for superiority will be presented.

The estimated within-group change from baseline and treatment difference at each post-baseline visit, obtained from the model, will be provided. The estimated within-group change and its standard error (SE) at each post-baseline visit will also be plotted by treatment group.

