### **8.3.2.2 Analysis Method**

#### **Absolute change from baseline in SwCl through Week 24:**

The estimand for the absolute change from baseline in SwCl through Week 24 is defined as the following:

- Treatment: VNZ/TEZ/D-IVA versus ELX/TEZ/IVA
- Population: Study population represented by inclusion and exclusion criteria
- Variable: Absolute change from baseline (after ELX/TEZ/IVA run-in) in SwCl through Week 24 (estimated by averaging Weeks 16 and 24)
- Handling of ICE: Same as the primary estimand (8.3.1.2)
- Population level summary: Difference in variable means between VNZ/TEZ/D-IVA and ELX/TEZ/IVA groups

The analysis of absolute change from baseline in SwCl through Week 24 will be based on an MMRM similar to the primary analysis of the primary estimand (8.3.1.3), with absolute change from baseline in SwCl at Day 15, Week 4, Week 16, and Week 24 as the dependent variable. The estimated treatment difference through Week 24 (estimated by averaging Weeks 16 and 24) will be presented along with the 2-sided 95% CI and *P* value. The estimated within-group change from baseline and treatment difference at each post-baseline visit, obtained from the model, will be provided. The estimated within-group change and its SE at each post-baseline visit will also be plotted by treatment group.

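### Minor, nearly free improvement: the primary MMRM holds the slope on baseline ppFEV1 constant from Day 15 to Week 24, which may cost a little precision at Weeks 16 and 24

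*Protocol*

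**What the plan says.** The protocol synopsis (Statistical Analyses) states: "The model will include treatment group, visit, and treatment-by-visit interaction as fixed effects". Protocol 12.3.3.1 gives the same model: "The model will include treatment group, visit, and treatment-by-visit interaction as fixed effects, with continuous baseline" ppFEV1, continuous baseline sweat chloride, age group and genotype group as covariates. SAP 8.3.1.3 keeps that form. Its list of categorical effects ends with "genotype group (F/F, F/G, F/RF, TCR/non-F), and treatment-by-visit interaction, with baseline" ppFEV1 and baseline sweat chloride as continuous covariates.

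The response is change from baseline at Day 15 and Weeks 4, 8, 16 and 24, with an unstructured covariance. The estimate is the average of Weeks 16 and 24.

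No section adds a baseline-by-visit term. The supplementary analysis (SAP 8.3.1.4) and the subgroup analyses (SAP 8.3.1.5) reuse the model. The key secondary analysis of sweat chloride "will be based on an MMRM similar to the primary analysis of the primary estimand (8.3.1.3"), and the Week 52 models in SAP 8.3.3.2 refer back in the same way.

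**The concern.** The plan leaves the treatment effect and the covariance unrestricted across visits but restricts the baseline slope to one value, and gives no reason for doing so. When change is regressed on its own baseline and variances are similar, the slope is about the correlation with baseline minus 1. If that correlation falls as visits move away from Day 1, the slope becomes steeper. The fitted common slope is a compromise across all five visits, so it would be too shallow at the two that define the endpoint.

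What is at stake is precision. Part of any chance baseline imbalance would stay in the estimate, and the interval would be a little wide. The same interval is later read against 0 for superiority, where the 3-point margin gives no cushion. No planned analysis would show whether the constant-slope assumption fits.

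**Working it through.** **Inputs from the documents.** The null hypothesis is that the new regimen "is inferior by >3 percentage points compared to ELX/TEZ/IVA". "The null hypothesis will be tested at a 1-sided significance level of 0.025". The planning statement reads "Assuming a within-group SD of 8 and 10% drop-out rate at Week 24", and it takes "a treatment difference of 0 between VX-121/TEZ/D-IVA and ELX/TEZ/IVA". There are 275 subjects per arm, and the stated power is above 95% from a two-sample t-test.

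**Assumed inputs.** The documents give no baseline SD, no correlations between visits and no slopes. Everything after step 1 rests on assumed values.

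**1. The plan's own figure.** Power ≈ Φ(3/SE − 1.96), with SE = 8·√(2/n).
- n = 275: SE = 0.682, power = Φ(4.40 − 1.96) = 99.3%.
- n = 247 (10% dropout): SE = 0.720, power = Φ(4.17 − 1.96) = 98.6%.

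The stated power is reproduced. It uses no covariate adjustment, so the slope specification does not affect it. The 95% half-width at n = 247 is 1.96 × 0.720 = 1.41 points.

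**2. Cost of a common slope, complete data.** Let b_t be the true slope at visit t, b_end the mean of the Week 16 and Week 24 slopes, and W the inverse residual covariance.
- Fitted common slope: g = (1′Wb)/(1′W1).
- Treatment estimate: raw difference − g × baseline imbalance.
- Excess variance per subject over visit-specific slopes: (b_end − g)² × SD_baseline².

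**3. Worked example.** Assume baseline SD 15, endpoint SD 8, and slopes −0.05, −0.07, −0.11, −0.18 and −0.25 at the five visits. Then b_end = −0.215 and g = −0.132.
- Visit-specific slopes: variance 64 − 0.215² × 225 = 53.6, SD 7.32, SE 0.659.
- Common slope: variance 53.6 + 0.083² × 225 = 55.15, SD 7.43, SE 0.668.
- SE ratio 1.014, so the interval is 1.4% wider. Power is 99.4% against 99.5%.
- A baseline imbalance as large as 1.96 SE (1.96 × 15 × √(2/247) = 2.65 points) moves the estimate by 0.083 × 2.65 = 0.22 point.

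**4. Range.**
- *Correlation structure assumed.* ppFEV1 was modelled as a stable part, a decaying part and noise, with baseline SD 12 to 20 and endpoint SD 6.5 to 9.3 (93 scenarios). The common slope was shallower than the Week 16/24 slope in every case. The SE was 0.1% to 4.7% larger, median 0.8%. On a half-width of 1.41 points that is 0.001 to 0.066 point, median 0.011. The median is worth 1 − 1/1.008² = 1.6% of the sample, about 9 of 550 subjects.
- *Slope drift imposed directly.* With baseline SD 10 to 20, the SE was 0.03% to 3.4% larger. The single exception, a drift from 0 to −0.30 with baseline SD 20, gave 7.6%. Power changed by less than 0.2 point throughout.

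**5. Simulation with dropout** (200 to 400 runs per scenario, baseline SD 15, sweat chloride slope set to 0).
- Dropout completely at random, or dependent on baseline equally in both arms: the two models' mean estimates agreed within 0.01 point, rejection at the margin was 2.0% to 3.3% for both, and the non-inferiority decision matched in 98.5% to 100% of runs. Monte Carlo error on the rejection rates is about 0.8 point.
- Stress case, with dropout depending on baseline in opposite directions by arm and averaging above 10%: for a true −3.0, the common slope gave −3.24 and −3.54, against −3.01 and −3.09 with the interaction. Decisions still matched in 99.0% and 97.5% of runs.

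**6. Cost if the slopes are equal.** One extra slope estimated from about 550 × 0.9 = 495 subjects inflates the variance by about 1/495, so the SE rises by about 1/(2 × 495) = 0.1%.

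**The case against.** The strongest reply is that this is a legitimate, prespecified choice, stated consistently in both documents. If ppFEV1 behaves as a stable level plus noise, the slope of change on baseline is the same at every visit and nothing is lost. If slopes flatten, the model over-adjusts. The 4-week run-in (Protocol 9.1.2 and 9.3.1) is meant to give a reliable on-treatment baseline, which makes near-constant slopes credible. Randomization is stratified on Day -14 ppFEV1 (Protocol 9.2), which should make imbalances smaller than the simple-randomization figure in step 3. All of this stands. It limits the point to a conditional, small gain in precision.

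A reader might also infer three stronger claims, which the documents do not support:
- *Baseline is under-adjusted at Weeks 16 and 24.* That holds only if slopes steepen with time. The documents give no slopes or correlations.
- *The same fault affects baseline sweat chloride in the ppFEV1 model.* The correlation-minus-1 argument applies to a variable's own baseline. It gives no reason for the sweat chloride slope to grow in a ppFEV1 model.
- *The primary estimate is biased.* Bias needs visit-varying slopes together with dropout whose relation to lung function differs by arm. The plan keeps subjects in follow-up after they stop treatment (Protocol 9.1.5.2) and uses their values under treatment policy (SAP 8.3.1.2), which limits such missingness.

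**Conclusion.** The point holds as a minor improvement. The constant slope on baseline ppFEV1 is a restriction that the plan neither needs nor explains. If correlation with baseline declines over time, the interval is about 0.1% to 4.7% wider than necessary, with a median of about 0.8%. These figures depend on the assumed baseline SD of 12 to 20, the endpoint SD near 8 and the assumed correlation structure, and another set of assumptions would move them. No corresponding figure was derived for the sweat chloride endpoint, where the point rests on the same logic alone. Neither the non-inferiority test nor the stated power is in question.

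**What to change.** Add a baseline ppFEV1-by-visit interaction to the primary MMRM (Protocol synopsis and 12.3.3.1, SAP 8.3.1.3). By the same logic, add baseline sweat chloride-by-visit to the sweat chloride MMRM (SAP 8.3.2.2). State whether the Week 52 models, which refer back to these, take the terms too. Baseline sweat chloride-by-visit in the ppFEV1 model is optional.

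SAP 8.3.1.3 currently responds to non-convergence by simplifying genotype and then the covariance. Put removal of the new interactions ahead of both steps.

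The cost is 4 parameters in the primary model (five visits) and 3 in the sweat chloride model (four visits), a line of SAP text for each and a small program change. No new data are needed, and the loss is about 0.1% of the SE if the slopes turn out to be equal.
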